9.5. Derived and transformed data

- Seronegative subjects:
 - Subjects with anti-HBs antibody concentration < 6.2 mIU/ml
- Seropositive subjects:
 - Subjects with anti-HBs antibody concentration ≥ 6.2 mIU/ml
- Seroprotected subjects:
 - Subjects with anti-HBs antibody concentration ≥ 10 mIU/ml

- Anamnestic response to the challenge dose is defined as:
 - At least (i.e. \geq) 4-fold rise in one month post-vaccination anti-HBs antibody concentrations in previously seropositive subjects.
 - In previously seronegative subjects, anti-HBs antibody concentrations ≥ 10 mIU/ml at one month post-challenge dose time-point.
- Amplitude of anamnestic response is the change in fold value from pre-challenge dose time-point to one month post-challenge dose.
- GMC calculations are performed by taking the anti-log of the mean of the \log_{10} concentration transformations. GMC will be calculated on all subjects. Antibody concentrations below the cut-off of the assay will be given an arbitrary value of half the cut-off for the purpose of GMC calculation.
- For a given subject and a given immunogenicity measurement, missing or non-evaluable measurements will not be replaced. Therefore, an analysis will exclude subjects with missing or non-evaluable measurements.

Safety/Reactogenicity:

For the analysis of solicited symptoms within 4 days (Days 0-3) post-challenge dose, missing or non-evaluable measurements will not be replaced. Therefore, the analysis of the solicited symptoms based on the TVC will include only subjects with documented safety data (i.e. symptom screen completed).

More specifically, the following rules will be used:

- Subjects who documented the absence of a solicited symptom after challenge dose will be considered not having that symptom after that dose.
- Subjects who documented the presence of a solicited symptom and fully or partially recorded daily measurement over the solicited period will be included in the summaries at the challenge dose and classified according to their maximum observed daily recording over the solicited period.
- Subjects who documented the presence of a solicited symptom after the challenge dose without having recorded any daily measurement will be assigned to the lowest intensity category at that dose (i.e. 37.5°C for fever or grade 1 for other symptoms).
- Doses without symptom sheets documented will be excluded.

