6.4.2. Additional considerations

6.4.2.1. Combined Solicited and Unsolicited Adverse Events

For clinicaltrial.gov and EudraCT posting purposes, a summary of combined solicited and unsolicited non-serious adverse events will be produced by System Organ Class and preferred terms and according to occurrence of each event.

A summary of subjects with all combined solicited (regardless of their duration) and unsolicited adverse events will be provided. Solicited adverse events will be coded by MedDRA as per the following codes

| Solicited symptom | Lower level term code | Corresponding Lower level term decode |
|-------------------|-----------------------|---------------------------------------|
| PA | 10022086 | Injection site pain |
| RE | 10022098 | Redness at injection site |
| SW | 10053425 | Swelling at injection site |
| FA | 10016256 | Fatigue |
| TE | 10016558 | Fever |
| GI | 10017944 | Gastrointestinal disorder |
| HE | 10019211 | Headache |

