11.2.5. Safety/Reactogenicity

- For the analyses of solicited symptoms, missing or non-evaluable measurements will not be replaced. Therefore, the analyses of the solicited symptoms based on the TVC will include only subjects with documented safety data (i.e. symptom screen completed).
- For the analyses of unsolicited adverse events/concomitant medication, all vaccinated subjects will be considered and subjects who did not report an event will be considered as subjects without an event.
- The maximum intensity of local injection site redness/swelling will be scored at GSK Biologicals as follows:

| | | |
|---|---|----------------------|
| 0 | : | Absent |
| 1 | : | ≤ 20 mm |
| 2 | : | >20 and ≤ 50 mm |
| 3 | : | > 50 mm |

- The maximum intensity of fever will be scored at GSK Biologicals as follows:

| Axillary | | |
|----------|---|-----------------------------------|
| 0 | : | < 37.5°C |
| 1 | : | ≥ 37.5 °C and ≤ 38.0 °C |
| 2 | : | > 38.0°C and ≤ 39.0 °C |
| 3 | : | > 39.0°C |

Note that for all tables described in this section, the way the percentage of subjects will be derived will depend on the event analysed (see table below for details). As a result, the N value may differ from one table to another.

| Event | N used for deriving % per subject for Vaccination phase | N used for deriving % per dose for Vaccination phase |
|---------------------------|--|--|
| Solicited general symptom | All subjects with at least one solicited general symptom documented as either present or absent (i.e., symptom screen completed) | All study visits with study vaccine administered and with at least one solicited general symptom documented as either present or absent (i.e., symptom screen completed) |
| Solicited local symptom | All subjects with at least one solicited local symptom documented as either present or absent (i.e., symptom screen completed) | All study visits with study vaccine administered and with at least one solicited local symptom documented as either present or absent (i.e., symptom screen completed) |
| Unsolicited symptom | All subjects with study vaccine administered | All study visits with study vaccine administered |
| Concomitant medication | All subjects with study vaccine administered | All study visits with study vaccine administered |

11.2.6. Number of decimals displayed:

The following decimal description from the decision rules will be used for the demography, immunogenicity and safety/reactogenicity.

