| | <each SOC> | <each PT term> | | | |
| Fatal SAE | At least one symptom | | | | |
| | <each SOC> | <each PT term> | | | |
| Related fatal SAE | At least one symptom | | | | |
| | <each SOC> | <each PT term> | | | |

HBV : Engerix-B challenge dose

At least one symptom = at least one symptom experienced (regardless of the MedDRA Preferred Term)

N = number of subjects with the administered dose

n* = number of events reported

n/% = number/percentage of subjects reporting the symptom at least once

CONFIDENTIAL

116811 (HBV-322)
Statistical Analysis Plan Final

Template 29 Listing of SAEs (Total Vaccinated Cohort)

| Group | Sub. | Case Id | Age at onset (Year) | Sex | Verbatim | Preferred term | System Organ Class | MED type | Dose | Day of onset | Duration | Intensity | Causality | Outcome |
|--------------|------|---------|------------------------|-----|----------|-------------------|-----------------------|-------------|------|-----------------|----------|-----------|-----------|---------|
| HBV group | | | | | | | | | | | | | | |

HBV : Engerix-B challenge dose

Dose = dose given prior to the serious adverse event

N/Y = No/Yes

Template 30 Listing of dropouts due to AEs, SAEs and solicited symptoms during the study period (Total vaccinated cohort)

| Study-Subject No. | Country | Gender | Race | AE Description | SAE | Causality | Outcome | Type of discontinuation |
|-------------------|---------|--------|------|----------------|-----|-----------|---------|-------------------------|
| | | | | | | | | |

HBV : Engerix-B challenge dose

Template 31 Solicited and Unsolicited symptoms experienced by at least 5 % of subjects classified by MedDRA Primary System Organ Class and Preferred Term within the 31-day (Days 0-30) post-vaccination - SAE excluded (Total Vaccinated cohort)

| HBV Group N = XXX | | | | | | |
|--|----------------------------------|--------|---|---|----|----|
| | | 95% CI | | | | |
| Primary System Organ Class (CODE) | Preferred Term (CODE) | n* | n | % | LL | UL |
| At least one symptom | | | | | | |
| Blood and lymphatic system disorders (10005329) | Leukocytosis (10024378) | | | | | |
| Cardiac disorders (10007541) | Angina unstable (10002388) | | | | | |
| | Mitral valve disease (10061532) | | | | | |
| | Myocardial infarction (10028596) | | | | | |
| Respiratory, thoracic and mediastinal disorders (10038738) | Pleural effusion (10035598) | | | | | |
| | Pneumothorax (10035759) | | | | | |

HBV : Engerix-B challenge dose

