At least one symptom = at least one symptom experienced (regardless of the MedDRA Preferred Term)

N = number of subjects with the administered dose

n* = number of events reported

n/% = number/percentage of subjects reporting the symptom at least once

95% CI = exact 95% confidence interval; LL = Lower Limit, UL = Upper Limit

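### Template 31, the combined table for registry posting, uses all dosed subjects as its only N, which conflicts with SAP 11.2.5 for the solicited rows and understates them if any symptom sheets are missing

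*SAP*

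**What the plan says.** SAP 6.4.2.1 introduces the table: "For clinicaltrial.gov and EudraCT posting purposes, a summary of combined solicited and unsolicited non-serious adverse events will be produced". It maps the seven solicited symptoms (pain, redness, swelling, fatigue, fever, gastrointestinal symptoms, headache) to MedDRA terms so that they can sit beside unsolicited events. It gives no denominator.

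The section does not cite a template by number, but Template 31 in SAP Annex 3 is the one mock table that fits. Its title begins "Solicited and Unsolicited symptoms experienced by at least 5 % of subjects classified by MedDRA Primary System Organ Class"; it covers Days 0-30, excludes SAEs and is set on the Total Vaccinated Cohort. It has one header N, footnoted "N = number of subjects with the administered dose".

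The derivation rules differ by type of event:

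- **Solicited symptoms.** SAP 11.2.5 says that "the analyses of the solicited symptoms based on the TVC will include only subjects with documented safety data". Its table of denominators repeats this separately for local and for general symptoms. Protocol 9.5, in its list of rules for the Days 0-3 solicited analysis, adds: "Doses without symptom sheets documented will be excluded".
- **Unsolicited events and concomitant medication.** Both documents use all vaccinated subjects and treat no report as no event.

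Templates 24 and 25 (solicited local and general symptoms) use subjects with a documented dose. So does Template 23, which also combines solicited and unsolicited symptoms and has separate N columns for any, general and local symptoms. SAP section 9 declares no change from the planned analyses.

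**The concern.** Template 31 carries the denominator meant for unsolicited events over to the solicited rows. A vaccinated subject with no symptom sheet enters N, but cannot enter the numerator for solicited pain, redness, swelling, fatigue, fever, gastrointestinal symptoms or headache. Missing information is thereby read as absence of the symptom, which SAP 11.2.5 is written to prevent.

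At stake is the accuracy of the public reactogenicity figures. If sheets are missing, a solicited rate in the posted table would be lower than the rate on documented subjects, always in the same direction, and the study report and the registry could show different figures for the same symptom. The rule for listing a row at 5% or more would also be applied to the lower figure.

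**Working it through.** **Inputs.** The plan gives no numerical figure for this point, so there is none to reproduce. The confidence interval method is Clopper-Pearson (SAP 11.1); the same routine returns the Protocol Table 18 limits for 72/80 (81.2 to 95.6) and 76/80 (87.7 to 98.6). Planned enrolment is about 100 (Protocol 4.1), so take V = 100 vaccinated. The number of missing sheets, m, is not in the documents; 1 to 20 is an assumed range. The numbers of reporters, n, are also assumed.

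**Formula.** Template 31 gives n/V. SAP 11.2.5 gives n/(V − m). The ratio is (V − m)/V = 1 − m/V, so the relative understatement equals the share of sheets missing, whatever n is. This holds for the solicited reports; a subject without a sheet could still enter a row through an unsolicited report.

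**Results, V = 100, n = 40.** Template 31 gives 40/100 = 40.0% (95% CI 30.3 to 50.3) throughout.

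| Sheets missing (assumed) | On documented subjects | 95% CI | Relative understatement |
|---|---|---|---|
| 0 | 40/100 = 40.0% | 30.3 to 50.3 | 0% |
| 1 | 40/99 = 40.4% | 30.7 to 50.7 | 1% |
| 5 | 40/95 = 42.1% | 32.0 to 52.7 | 5% |
| 10 | 40/90 = 44.4% | 34.0 to 55.3 | 10% |
| 20 | 40/80 = 50.0% | 38.6 to 61.4 | 20% |

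With n = 20, Template 31 gives 20.0%, against 20.2%, 21.1%, 22.2% and 25.0% for m = 1, 5, 10 and 20.

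**The 5% filter.** A row is lost only if n/V < 0.05 ≤ n/(V − m), that is, if V − m ≤ 20n < V.

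- V = 100: the largest multiple of 20 below 100 is 80, so m must be at least 20. Then 4/80 = 5.0% would be listed but 4/100 = 4.0% would not. With 10 or fewer sheets missing, no row changes.
- V = 101 to 105: five reporters fall below 5% on all dosed subjects (5/101 = 4.95%) but reach 5% once documented subjects number 100 or fewer (5/100 = 5.0%; 5/95 = 5.3%). This turns on V landing just above 100.

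**The case against.** The strongest defence is that Annex 3 describes its displays, titles and footnotes as illustrative and open to adaptation, and says they were copied from another study. SAP 11.2.5, the operative text, already says that the percentage depends on the event analysed and that N may vary between tables. On that view the right denominator for each event type is fixed, and all dosed subjects is the correct N for the unsolicited rows.

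This narrows the point but does not remove it. SAP 11.2.5 allows N to differ from table to table; it does not say what to do when one table holds both types of event. The footnote is therefore the only specific instruction, and Annex 3 lets minor template changes pass without a SAP amendment, so the choice could be made in programming and leave no record.

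Other parts of the defence do stand, and they rule out stronger readings that a reader might infer:

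- **That the posted rates are biased.** They would be only if sheets are missing. No return rate is given, and Protocol 5.6.17 has sites pursue unreturned diary cards. The 20% in Protocol 9.3 concerns evaluability for the immunogenicity sample size and is not a sheet non-return rate.
- **That any mismatch with Template 25 shows the denominator error.** The protocol glossary makes a solicited symptom with onset after the solicited period an unsolicited event. Headache, fatigue or fever in Template 31 can therefore include Day 4-30 onsets that Template 25 leaves out, and the rows can differ even with the right N.
- **That the protocol's exclusion rule forbids this table.** That rule is listed under the Days 0-3 solicited analysis, while Template 31 is a Days 0-30 summary added for posting. The clear conflict is with SAP 11.2.5, whose sentence carries no day window.

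Template 22 also reports sheet compliance, so a reader of the full report could see the size of any shortfall.

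**Conclusion.** The point holds as an inconsistency within the SAP: one N for mixed content, contrary to SAP 11.2.5 for the solicited rows, with no rule for a combined table. The understatement equals the share of sheets missing. With 5 missing of 100 and 40 reporters, both assumed, the difference is 2.1 percentage points, well inside the interval around 40.0%. It is zero with full return and probably small in practice. A reader might infer that solicited symptoms would routinely drop out of the public table; the arithmetic does not support that, since it takes about 20 missing sheets at V = 100, or a V just above 100. The primary endpoint and Templates 24 and 25 are unaffected, and all analyses are descriptive. It merits a correction because the table is public and the remedy is cheap.

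**What to change.** Amend SAP 6.4.2.1 and the Template 31 footnote so that the denominator is set in advance by symptom, not by which reports happen to occur:

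1. For terms mapped from the seven solicited symptoms, use subjects with the relevant (local or general) symptom screen completed. Where late-onset unsolicited reports fall under the same term, show the solicited Days 0-3 reports and the unsolicited reports as separate rows, each on its own N.
2. For all other terms, use all dosed subjects.
3. State the N for the overall row that counts subjects with any symptom. Template 23, with its documented-dose N, is a precedent within this SAP.
4. Apply the 5% filter to the percentage on the stated N.
5. Footnote each N.

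The cost is a SAP text change and minor programming; no new data are needed. The drawback is that rows in one table carry different Ns, as the columns of Template 23 are already laid out to allow.
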